6.3 Measures to Minimise Bias: Randomization and Blinding

This is an open-label study; no blinding is required. Each potential participant is assigned a unique participant identification number at the screening visit after signing consent. Once a participant is assigned a unique identification number, it cannot be reused for another participant. Study intervention will be dispensed at the study visits summarised in the relevant Substudy. Returned study intervention should not be re-dispensed to the participants.

If an unscheduled assessment is performed, and the participant has not progressed, every attempt should be made to perform the subsequent assessments at their scheduled visits. This schedule is to be followed to minimise any unintentional bias caused by some participants being assessed at a different frequency than other participants.

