Abbreviations: AE = adverse event; ALT = alanine aminotransferase; aPTT = activated partial thromboplastin time; CD8 = cluster of differentiation 8; CT = computed tomography; DNA = deoxyribonucleic acid; ECG = electrocardiogram; ECOG = Eastern Cooperative Oncology Group; GDF15 = growth differentiation factor 15; HbA1c = haemoglobin A1c; HIV = human immunodeficiency virus; IRT = interactive response technology system; INR = international normalised ratio; MRI = magnetic resonance imaging; NSCLC = non-small-cell lung carcinoma; CCl cell; PET = positron emission tomography; PT = prothrombin time; PID = participant identification number; RECIST = response evaluation criteria in solid tumours; RNA = ribonucleic acid; SAE = serious adverse event; T3 = triiodothyronine; T4 = thyroxine; TSH = thyroid-stimulating hormone; V = visit; WOCBP = woman of childbearing potential.

Table 13 Schedule of Activities – Study Visits

Visit Number	,	V2	V3	V4	V5	V6	V7	V8	V9	V10	V11	V12	V13-Vn	Details in Section
Procedure/Study Day	D1 Pre- Dose	D1 Post- Dose	D2	D8	D15	D22	D29	D36	D43	D64	D85	D106	D127+ Q3W	
Week	1	1	1	2	3	4	5	6	7	10	13	16	19+	
Cycle Number and Cycle Day ^a	C1D1	C1D1	C1D2	C1D8 (±1D)	C1D15 (±1D)	C2D1 (±1D)	C2D8 (±1D)	C2 D15 (±1D)	C3D1 (±3D)	C4D1 (±3D)	C5D1 (±3D)	C6D1 (±3D)	C7D1-CnD1 (±3D)	
Eligibility	Į.	1			1	I .	1			Į.	ll .	I .	II.	1
Confirm eligibility for enrolment in Main Study	X													10.5.1; 10.5.2
Study Procedures	and Exar	ninations			•									
Physical examination, including appetite assessment	X			X	X	X	X °	X °	X	X	X	X	X	8.2.1
Local 12-lead ECG	X	X				X			X				X Q12W	10.8.2.1 Table 17
Vital signs, including body weight	X	X d		X	X	X	X °	Χ°	X	X	X	X	X	8.2.3
ECOG Performance Status	X			X	X	X	X °	X °	X	X	X	X	X	8.2.2
Assessment of AEs/SAEs	X	X	X	X	X	X	X c	X c	X	X	X	X	X	8.3

Visit Number	•	V2	V3	V4	V5	V6	V7	V8	V9	V10	V11	V12	V13-Vn	Details in Section
Procedure/Study Day	D1 Pre- Dose	D1 Post- Dose	D2	D8	D15	D22	D29	D36	D43	D64	D85	D106	D127+ Q3W	
Week	1	1	1	2	3	4	5	6	7	10	13	16	19+	
Cycle Number and Cycle Day ^a	C1D1	C1D1	C1D2	C1D8 (±1D)	C1D15 (±1D)	C2D1 (±1D)	C2D8 (±1D)	C2 D15 (±1D)	C3D1 (±3D)	C4D1 (±3D)	C5D1 (±3D)	C6D1 (±3D)	C7D1-CnD1 (±3D)	
Concomitant medications	X		X	X	X	X	X c	X c	X	X	X	X	X	6.5
Disease Assessmen	ts													
Disease assessment by RECIST v1.1 and SMI assessment °									X D1-D7			X ^f W15 D1-D7	W24±6D then Q9W±6D until W52, then Q12W±6D	10.8.1

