- Whole body PET imaging to occur before the initial dosing of study intervention (≤ 14 day) on Cycle 1 Day 1. Imaging to be done only after the participant's eligibility for the study has been confirmed. PET imaging must be before pre-treatment biopsy. CD8+ PET Tracer [89Zirconium (Zr)-deferoxamine (Df)-crefmirlimab] to be ordered at least 72 hours before administration and PET imaging appointments should be booked accordingly. Tracer to be administered preferably 24 (±3) hours but not more than 72 hours prior to whole body PET imaging. The duration between administration of the tracer and the PET scan should be the same at screening and at Day 29. If a participant holds or discontinues treatment prior to Day 29, if able, the participant should still have the PET scan as scheduled.

Abbreviations: ADA = antidrug antibody; AE = adverse event; CR = complete response; CT= computed tomography; D = Day; DNA= deoxyribonucleic acid; ECG = electrocardiogram; ECOG = eastern cooperative oncology group; EOT = end of treatment; GDF15 = growth differentiation factor 15; HbA1c = haemoglobin A1c; MRI = magnetic resonance imaging; n = visit number; NSCLC = non-small-cell lung cancer; CC ; PK = pharmacokinetic; PR = partial response; Q3W = every 3 weeks; Q6W = every 6 weeks; Q9W = every 9 weeks; Q12W = every 12 weeks; Q26W = every 26 weeks; RNA = ribonucleic acid; RECIST = response evaluation criteria in solid tumours; SAE = serious adverse event; SD = stable disease; T3 = triiodothyronine; T4 = thyroxine; TSH = thyroid-stimulating hormone; V = visit; WOCBP = woman of childbearing potential.

Table 14 Schedule of Activities – End of Treatment

Study Period	EOT	Follow-u	p Post EOT	LTFU	Details in
Procedure/Study Day		Day 30 (± 7 days)	Day 90 (± 7 days)	Q12W Post Day 90 Visit	Section
		Post EOT	Post Last Dose		
Study Procedures and Examinations			•		
Physical examination, including appetite assessment	X	X	X		8.2.1
ECOG performance status	X	X	X		8.2.2
Local 12-lead ECG (triplicate)	X				8.2.4
Vital signs, including body weight	X	X	X		8.2.3
Assessment of AEs/SAEs	X	X	X		8.3
Concomitant medications	X	X	X		6.5
Disease Assessments				1	
Disease assessment by RECIST v1.1 and SMI assessment ^a	X b		X c	Х°	10.8.1
CT or MRI, brain (Required for participants with known brain metastasis and as clinically indicated for other participants)	X b		X °	X °	10.8.1
Safety Laboratories			1	1	
Clinical chemistry	X	X			8.2.5
Haematology	X	X			8.2.5
HbA1c	X	X			8.2.5

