Thyroid function tests (TSH, free T4, free T3) ^d	X	X			8.2.5
Urinalysis	X	X			8.2.5
Coagulation parameters (PT/aPTT/INR/d-Dimer/Fibrinogen)	X	X			8.2.5
Pregnancy test (WOCBP) °	X	X	X		8.2.5
Virology (Hepatitis B and C) ^f		X			8.2.5
Biomarker Evaluations		1		. 	
CCI	Collect on progression				10.8.6.1.3

Study Period	ЕОТ	Follow-u	p Post EOT	LTFU	Details in	
Procedure/Study Day		Day 30 (± 7 days)	Day 90 (± 7 days)	Q12W Post Day 90 Visit	Section	
		Post EOT	Post Last Dose			
Serum for GDF15 target engagement	X	X	X		10.8.5.3.1	
Whole blood for CCI (refrigerated)	X	X	X		10.8.6.4	
Whole blood for flow cytometry	X	X	X		10.8.6.5	
CCI	X	X	X		10.8.6.3	
CCI	X	X	X		10.8.6.7	
CCI	X	X	X		10.8.6.7	
Plasma for circulating tumour DNA	X	X	X		10.8.6.6	
PK and Immunogenicity	 		•			
Parts A, B and C: AZD8853 PK			X		10.8.5.1 Table 18	
AZD8853 ADA	X	X	X		10.8.5.2 Table 19	
EOT and Follow-up Assessment	'	'	•			
Subsequent anti-cancer therapy	X	X	X	X	8.2.8	
Survival status (by telephone, email, or clinic visit)	X	X	X	X	8.2.8	

To include CT or MRI slices through T12 and L3.

Abbreviations: ADA = antidrug antibody; AE = adverse event; aPTT = activated partial thromboplastin time; CT = computerized tomography; DNA = deoxyribonucleic acid; ECG = electrocardiogram; ECOG = Eastern Cooperative Oncology Group; EOT = end of treatment; GDF15 = growth differentiation factor 15; INR = international normalised ratio; LTFU = long Term Follow-up; MRI = magnetic resonance imaging; NSCLC = non-small-cell lung cancer; CC | PK = pharmacokinetics; PT = prothrombin time; Q12W = every 12 weeks; RNA = ribonucleic acid; RECIST = Response Evaluation Criteria in Solid Tumours; SAE = serious adverse event; T3 = triiodothyronine; T4 = thyroxine; TSH = thyroid-stimulating hormone; WOCBP = woman of childbearing potential.

b If CT or MRI scan for disease assessment is performed ≤ 14 days prior to the EOT visit, it will not be required at EOT visit.

^c Will not be performed if previously confirmed disease progression has been documented.

d Free T4 and T3 measured if TSH is abnormal or if clinical suspicion of an AE related to the endocrine system.

^e A urine or serum pregnancy test is acceptable; if urine test is equivocal or positive then serum β-hCG testing should be performed for confirmation.

f Required for participants with a history of hepatitis B or hepatitis C.

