This appendix details the implementation of RECIST v1.1 guidelines (Eisenhauer et al, 2009). Investigator assessments will use the RECIST v1.1 guidelines described in this appendix.

Imaging modalities and acquisition specifications for RECIST v1.1

A summary of the imaging modalities that can be used for tumour assessment TLs, NTLs, and NLs is provided in Table 23.

Table 23 Summary of Imaging Modalities for Tumour Assessment

Target Lesions	Non-Target Lesions	New Lesions
CT	CT	CT
MRI	MRI	MRI
	Plain X-ray	Plain X-ray
	Chest X-ray	Chest X-ray
		Bone scan (Scintigraphy)
		FDG-PET/CT

Abbreviations: CT = Computed tomography; FDG-PET/CT = ¹⁸F-Fluoro-deoxyglucose positron emission tomography/CT; MRI = Magnetic resonance imaging.

CT and MRI

Computed tomography with i.v. contrast is the preferred imaging modality (although MRI with i.v. contrast is acceptable if CT is contraindicated) to generate reproducible anatomical images for tumour assessments (ie, for measurement of TLs, assessment of NTLs, and identification of NLs). It is essential that the same correct imaging modality, image acquisition parameters (eg, anatomic coverage, imaging sequences, etc.), imaging facility, tumour assessor (eg, radiologist), and method of tumour assessment (eg, RECIST v1.1) are used consistently for each participant throughout the study. The use of the same scanner for serial scans is recommended, if possible. It is important to follow the image collection/tumour assessment schedule as closely as possible (refer to the Schedules of Activities [SoAs; Table 12, Table 13, and Table 14]), and this on-study imaging schedule MUST be followed regardless of any delays in dosing or missed imaging visits. If an unscheduled assessment is performed (eg, to investigate clinical signs/symptoms of progression) and the participant has not progressed, every attempt should be made to perform the subsequent scan acquisitions at the next scheduled imaging visit.

Due to its inherent rapid acquisition (seconds), CT is the imaging modality of choice. Body

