#### **4.2.6.2 Derivations**

$$\text{PFS (Months)} = \frac{(\text{Date of PFS event or censoring}-\text{date of first dose of IP})+1}{\left(\frac{365.25}{12}\right)}$$

where PFS event is progression or death.

Participants who have not progressed or died at the time of analysis are censored at the time of the latest date of assessment from their last evaluable disease assessment. However, if the participant progresses or dies immediately after two or more consecutive missed visits, the participant is censored at the time of the latest evaluable disease assessment prior to the two missed visits. Note: a NE visit is not considered as a missed visit.

Given the scheduled visit assessment scheme (i.e., first visit at week six, then nine-weekly for till 52 weeks then twelve-weekly thereafter) the definition of 2 missed visits changes.

If the previous RECIST v1.1 assessment is less than study day 288 (i.e. study week 42) and greater than study day 99 (study week 15), then two missed visits equates to 20 weeks since

the previous RECIST v1.1 assessment, allowing for early and late visits (i.e.  $2 \times 9$  weeks + 1 week for an early assessment + 1 week for a late assessment = 20 weeks).

If the previous RECIST visit is after the visit assessment at study week 6 or study week 15, then two missed visits equate to:

- 15 weeks (105 days), if study week 6 (5 weeks after 1st IP dose) and study week 15 (14 weeks after 1st IP dose) are the two consecutive visits missed [ $(1 \times 5 \text{ weeks}) + (1 \times 9 \text{ weeks}) + 1 \text{ week for late assessment}$ ].
- 19 weeks (133 days), if study week 15 (14 weeks after 1st IP dose) and week 24 (23 weeks after 1st IP dose) are the two consecutive visits missed [ $(1 \times 9 \text{ weeks}) + (1 \times 9 \text{ weeks}) + 1 \text{ week for late assessment}$ ].

If the two missed visits occur over the period when the scheduled frequency of RECIST v1.1 assessments changes from nine-weekly to twelve-weekly this equates to 23 weeks (i.e. take the average of 9 and 12 weeks which gives 10.5 weeks and then apply same rationale, hence  $2 \times 10.5 \text{ weeks} + 1 \text{ week for an early assessment} + 1 \text{ week for a late assessment} = 23 \text{ weeks}$ ). The time period for the previous RECIST v1.1 assessment is from study days 288 to 351 (i.e., study week 42 to study week 51).

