## 7 APPENDICES

### 7.1 Appendix A RECIST

#### **Derivation of RECIST v1.1 Visit Responses**

For all participants, the RECIST v1.1 tumour response data is used to determine each participant's visit response according to RECIST version 1.1. It is also used to determine if and when a participant has progressed in accordance with RECIST version 1.1 and their best objective response to IP.

Baseline radiological tumour assessments are performed no more than 28 days before the start of IP and ideally as close as possible to the start of IP. Tumour assessments are performed 6 weeks after 1st IP then every 9 weeks, until week 52 then every 12 weeks until disease progression.

If an unscheduled assessment is performed, and the participant has not progressed, every attempt is made to perform the subsequent assessments at their scheduled visits. This schedule is followed in order to minimize any unintentional bias caused by some participants being assessed at a different frequency than other participants.

From the investigator's review of the imaging scans, the RECIST v1.1 tumour response data is used to determine each participant's visit response according to RECIST version 1.1. At each visit, participants are programmatically assigned a RECIST version 1.1 visit response of CR, PR, SD, or Progressive Disease, using the information from TLs, NTLs and new lesions and depending on the status of their disease compared with baseline and previous assessments. If a participant has had a tumour assessment that cannot be evaluated, then the participant is assigned a visit response of NE (unless there is evidence of progression in which case the response is assigned as Progressive Disease).

Please refer to [Table 10](#) for the definitions of CR, PR, SD and Progressive Disease.

RECIST v1.1 outcomes (i.e. PFS, ORR etc.) are calculated programmatically for the site investigator data (see last section of this Appendix) from the overall visit responses.

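### SAP Table 8 has no off-treatment row, so in year 1 one missed 12-weekly follow-up scan is censored as if two had been missed

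*Protocol*

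**What the plan says.** **On treatment.** Protocol Table 13 schedules RECIST scans from Cycle 1 Day 1. After the Week 6 and Week 15 assessments the entry is "W24±6D then Q9W±6D until W52, then Q12W±6D".

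**Off treatment.** Protocol Section 7.1 requires scans to go on after AZD8853 is stopped before progression, and refers to the Substudy schedule of activities. Table 14 is the schedule for that period. It marks a RECIST scan at EOT, at Day 90 (± 7 days) after the last dose, and in a long-term follow-up column headed "Q12W Post Day 90 Visit". No scan is marked at Day 30. One footnote waives the EOT scan: "If CT or MRI scan for disease assessment is performed ≤ 14 days prior to the EOT visit". Another limits the later scans to participants who are still progression-free: "Will not be performed if previously confirmed disease progression has been documented".

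**Analysis.** SAP 4.2.6.2 defines PFS to include events after treatment stops, and builds its missed-visit rule on one schedule: "first visit at week six, then nine-weekly for till 52 weeks then twelve-weekly thereafter". SAP Appendix A describes the same schedule: "then every 9 weeks, until week 52 then every 12 weeks until disease progression". Neither has an off-treatment branch. SAP Table 8 turns the schedule into fixed windows. If an event comes later than the window after the previous scan, it is replaced by censoring at that scan. SAP Table 9 states the principle differently: censor after two or more consecutive assessments are missed on the schedule that the protocol specifies.

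**The concern.** For a progression-free participant off treatment in the first year, the schedule in force is Table 14, while the windows come from Table 13. The Table 14 interval is longer, so a window sized to detect two missed 9-weekly scans can be exceeded by one missed 12-weekly scan. A progression that was observed and dated is then recorded as censored, against the SAP's own Table 9. DoR ends on the PFS event or censoring date (SAP 4.2.5.2), and duration of stable disease, which feeds DCR at study week 15, uses the same dates (SAP 4.2.4.2). Separately, wider scan spacing off treatment means that progression is recorded later there than on treatment.

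**Working it through.** **1. Reproduce Table 8.** The SAP's formula is the sum of the next two intervals plus the visit-window allowance, in weeks × 7.

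| Previous scan (study day) | Formula | Window |
|---|---|---|
| Baseline or none | (5 + 9 + 1) × 7 | 105 days |
| 36 (Week 6) | (9 + 9 + 1) × 7 | 133 days |
| >99 to 288 | (2 × 9 + 2) × 7 | 140 days |
| >288 to 351 | (2 × 10.5 + 2) × 7 | 161 days |
| >351 | (2 × 12 + 2) × 7 | 182 days |

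The day anchors also reproduce: (week − 1) × 7 + 1 gives 36, 99, 288 and 351 for Weeks 6, 15, 42 and 51. Table 8 has no row for scans on days 37 to 99; I take 133 days for them.

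**2. Table 14 dates.** With last dose on study day L, scans fall at EOT, L + 90, L + 174, L + 258, and so on. With no scan missed, the largest gap I find is 97 + 14 = 111 days (a scan 14 days before an EOT visit held on the day of last dose, then Day 90 at +7). This is below 133, so full attendance does not trigger the rule.

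**3. One missed long-term follow-up scan.** The gap is 2 × 84 = 168 days, above 133, 140 and 161 but below 182. Example: last dose Day 43; Day 90 scan on study day 133; the scan due on Day 217 is missed; progression is found on Day 301. The gap is 301 − 133 = 168 against a window of 140, so the event is censored at Day 133.

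If the Day 90 visit moves by ± 7 days and later scans keep their nominal dates, the gap is 161 to 175 days: always above 140, and at or above 161. If follow-up scans also vary by ± 6 days (an assumption, since Table 14 gives no window for them), it is 155 to 181 days: still above 140, but not always above 161.

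**4. A missed Day 90 scan.** If the EOT scan is e days after last dose, the gap to the next scan is 174 − e. For e = 21 it is 153 days (above 140, below 161). For e = 35 it is 139 days (above 133, below 140). The documents do not fix e, so the result depends on it.

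**5. Deaths.** After one missed long-term follow-up scan, a death before the next scan is censored only if it falls beyond the window: days 141 to 168 after the previous scan where the window is 140.

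**6. Direction of the censoring effect.** Moving an event at time t back to censoring at time c takes a progression-free person out of the risk set between c and t. Kaplan–Meier then spreads that person's weight over everyone still at risk after c. The curve is lower or unchanged before t, and higher or unchanged after t.

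Size for one such participant among 40, using the example in step 3 and assuming exponential PFS with no other censoring in the other 39. With a median of 110 days, the expected number of others at risk is 39 × 2^(−133/110) = 16.87 at Day 133 and 39 × 2^(−273.9/110) = 6.94 at 9 months.
- Event kept: PFS-9 = (6.94 + 1)/40 = 19.9%.
- Event censored: PFS-9 = (17.87/40) × (6.94/16.87) = 18.4%.

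Over medians of 90 to 130 days the change is −0.6 to −0.8 percentage points at 6 months, −1.3 to −1.7 at 9 months and +0.4 to +0.7 at 12 months.

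**7. DCR.** The threshold is 14 weeks = 98 days. Take last dose on Day 1, stable disease at the Day 90 scan (study day 91), the Day 175 scan missed, progression on Day 259, and no subsequent therapy. The gap is 168 against 133. Duration of stable disease falls from 259 to 91 days, and the participant changes from disease control to none. When the previous scan is later than this threshold, as in step 3, DCR does not change.

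**8. Detection delay.** If progression is equally likely at any point in an interval, the mean delay is 84/2 = 42 days off treatment and 63/2 = 31.5 days on treatment, a difference of 10.5 days.

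**The case against.** **Table 13 scans may continue off treatment.** Section 7.1 says that visits and data collection carry on under the protocol after discontinuation. On that reading a participant who skips a 12-weekly scan has also skipped 9-weekly ones, and the windows are right. This is possible but weak. Table 14 has its own RECIST columns and does not mention Table 13 scans running alongside. Section 8.1 ties the return to scheduled scans, after an off-window scan, to the time on study treatment. If this reading was meant, the protocol needs to say so.

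**Table 9 already gives the right rule.** Its wording covers Table 14, so one missed scan counts as one. That is true, but Table 8 supplies the numbers that will be programmed, and the two then disagree.

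**A reader might infer more than the documents support:**
- *That protocol Appendix F conflicts with Table 14.* It does not. It gives no 9-week interval and cites Tables 12, 13 and 14. Its sentence "this on-study imaging schedule MUST be followed regardless of any delays in dosing or missed imaging visits" concerns delays and missed visits, not discontinuation.
- *That Section 6.3 rules out the Table 14 schedule.* The aim to "minimise any unintentional bias caused by some participants being assessed at a different frequency than other participants" appears in a paragraph on returning to schedule after an unscheduled assessment. It shows the intent, but does not set an off-treatment interval.
- *That any missed follow-up scan counts as two.* Steps 4 and 5 show that this depends on the EOT scan date or the death date.
- *That the censoring lengthens PFS.* Step 6 shows a lower or unchanged curve before the true event time. Only the detection delay lengthens recorded PFS throughout.

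**The endpoint is descriptive.** This stands. PFS is secondary, there are no hypotheses, and cohorts are not compared.

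**Conclusion.** The conflict is real, and a stated rule gives a wrong result. With Table 14 as the off-treatment schedule and the previous scan at or before study day 351, one missed 12-weekly scan followed by progression at the next nominal scan is censored (168 days against 133, 140 or 161), contrary to SAP Table 9. After day 351 the 182-day window fits.

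The effect is small. The documents do not say how many participants will stop before progression or miss a scan. If 10–20% stop before progression (4 to 8 of 40) and 10–20% of those miss a follow-up scan, at most 0.4 to 1.6 of 40 per expansion are affected, and each must also have an event beyond the window. One such case moves a landmark PFS estimate by up to about 1.7 percentage points under the assumptions in step 6, down before the true event time and up after it. The 10.5-day detection delay, averaged over an expansion at the same 10–20%, is about 1 to 2 days. DoR carries the same censoring, and DCR changes only when the previous scan falls short of 14 weeks. ORR and error rates are untouched. The point merits correction because the repair is cheap.

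**What to change.** Reconcile Table 14 with the SAP by stating which scan schedule applies to progression-free participants off treatment.

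If Table 14 stands, amend SAP 4.2.6.2 and Table 8. After treatment discontinuation, two missed visits should be determined from the Table 14 assessments due after the last evaluable scan, whichever table that scan came from. There are two ways to do this:
- **Count the Table 14 scans actually missed.** This follows Table 9 directly and is correct for any EOT timing.
- **Use 2 × 12 + 2 = 26 weeks (182 days)** when the missed assessments fall on the Day 90 and 12-weekly schedule. One missed follow-up scan (168 days) then passes and two (3 × 84 = 252 days) are caught. The margin is thin when the EOT scan is waived: a scan 14 days before an EOT visit on the day of last dose, with Day 90 missed, gives 174 + 14 = 188 days. Counting avoids this.

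If 9-weekly scanning is meant to continue off treatment, Table 14 should say so. One missed scan is then 126 days (138 with ± 6-day windows), which the existing 140-day window handles.

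The SAP route costs one more derivation rule, which uses the treatment discontinuation date, and no extra scans. The protocol route costs a Table 14 change and more frequent scans off treatment in year 1.
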